As noted in Section 3, it is likely that the spectrum of lung diseases associated with HIV infection will change as antiviral therapy and various preventive treatments for P. carinii pneumonia and tuberculosis become more widely applied. Having a prospective surveillance system in place in which a uniform series of diagnostic studies is applied in a defined manner over a period of several years should serve to identify changes in the absolute and relative frequencies of the lung diseases associated with HIV infection.

Although the existing data strongly suggest a broader range of lung diseases associated with HIV infection than is currently recognized, it is not clear that infection with HIV is the only determining factor in all instances. It is possible that the apparent increased incidence of processes such as pyogenic pneumonias, tuberculosis, lymphocytic alveolitis, etc. may be related to "lifestyles" or practices such as intravenous drug use, inhalation of nitrates, or other as yet unidentified factors. For example, it is well established that both intravenous and inhalational drug use cause lung

disease. Thus, establishing associations between HIV infection and the various nonAIDS-defining lung diseases necessitates evaluation of persons from HIV transmission categories who do not have HIV infection.

Inclusion of an HIV seronegative control group not only enables comparisons of the incidence of various lung diseases, but also provides inferential information concerning the possibility of HIV itself causing lung disease. If there is an excess prevalence of respiratory symptoms, radiographic findings and abnormalities in pulmonary function tests that cannot be attributed to identifiable lung diseases, one inference would be that HIV itself was causing the findings. Such an observation would provide the rationale for a more specific directed study seeking to answer the question, "Is HIV a direct cause of lung disease?".

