7.2.3 Scheduled follow-up evaluations

Table 6 shows the evaluations to be performed and their frequencies in each of the groups. During these evaluations a modified history and physical examination will be done and the same series of laboratory tests as performed in the initial evaluation (except induced sputums) will be obtained. For purposes of data analysis subjects will be considered as belonging to the group to which they were originally assigned. Subjects in Groups A-1, B-1 and C who develop an HIV-related pulmonary process will continue to be followed at the same intervals except that pulmonary function tests will be performed every 6 months. HIV seronegative controls (Group C) will be followed at the same intervals as Groups A-1 and B-1. The schedule for Group C subjects who become HIV seropositive will not change.

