7.2.4 Diagnostic evaluation of symptoms or findings suggestive of lung disease

All diagnostic evaluations will be performed in the Clinical Centers and will follow the algorithms devised for purposes of the protocol (Section 7.2.7). The diagnostic evaluation may be triggered by the occurrence of symptoms (noted either at the time of a scheduled evaluation or between evaluations) or by chest radiograph detected on scheduled screening examinations. Standard methods to be used for each of the studies are described in Appendix 5. All data will be recorded on standard forms.

The symptoms that will trigger an evaluation include:

Table 6
Schedule of Interval Laboratory Studies

Frequency of studies (months)
(See text for definitions of group)

Study	Group A-1(1)	Group A-2	Group B-1(1)	Group B-2	Group C(1)	1-month F/U (all groups)(2)
History Performance status	6	3	6	3	6	+
Physical Exam	6	3	6	3	6	+
CBC/Diff, platelets	6	3	6	3	6	+
ESR/SMA	6	3	6	3	6	+
Absolute CD-4 CD-8, CD-3(4)	6	3	6	3	6	+
Serum Bank	6	3	6	3	6	+
HIV Ab(3)	Entry	Entry	Entry	Entry	6	0
Induced Sputum	Entry	Entry	Entry	Entry		
Skin tests	12	12	12	12	12	0
PFT	12	3	12	3	12	+
CXR (PA/Lat)	12	3	12	3	12	+

(1) Subjects enrolled in Group A-1 or B-1 who later develop an HIV-related pulmonary complication will continue the same schedule, except PFT's will be performed every 6 months. The schedule of evaluations for Group C subjects who seroconvert will not change.

(2) "+" = test performed.

(3) Omit if documented positive prior to study entry.

(4) May be omitted if performed within the three months prior to visit.

1) unexplained cough that persists for more than five days;
2) unexplained breathlessness (progressive over ≥ 5 days or severe ≥ 1 day); or 3) unexplained new onset of documented fever ($\geq 38^{\circ}\text{C}$ oral ≥ 5 days). As a part of the orientation and at each routine clinic visit, each study subject will be alerted to these symptoms and instructed to contact the study office should they develop. For each of these symptoms, if a reason other than a possible HIV-related pulmonary process can be found (e.g., asthma), the evaluation will not proceed. If the subject has fever with localizing extrapulmonary symptoms (e.g., diarrhea) and no pulmonary symptoms, the evaluation will not proceed, and the subject will be referred to the primary physician. Any diagnoses resulting from such an episode will be entered at the subsequent visit on the Interval Visit Questionnaire.

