Symptom Evaluation: When symptoms are reported the subject will be scheduled for a Symptom Evaluation Visit. These evaluations may be performed either on an inpatient or outpatient basis depending on the severity of symptoms and logistics of the evaluation.

The symptom evaluation visit will include:

1. Interval Visit Questionnaire.
2. Physical examination. The physical examination will be the same as that performed for the routine visits. The methods for procedures 3 through 7 are described in Appendix 5.
3. Chest radiograph (frontal and lateral views). If a radiographic abnormality is found, further evaluation will proceed as outlined in Section 7.2.7. Patients with cough and/or shortness of breath and no radiographic findings will have pulmonary function tests performed. Patients with fever but no specific pulmonary symptoms and normal chest films will be referred to their primary physicians and scheduled for a one month follow-up visit.

Based on the results of the history, physical examination, and chest radiograph, the physician investigator may make the clinical decision that the subject has acute bronchitis and elect to empirically treat the patient with antibiotics or simply observe him/her without proceeding to the items listed below. Otherwise, the following sequence of studies will be done:

4. Pulmonary function tests (lung volumes, expiratory flows and the single breath diffusing capacity for carbon monoxide (DLCO)).
Abnormalities in pulmonary function such as airways obstruction, or bronchitis, may account for the patient's symptoms. The subject will be scheduled for a one month follow-up visit.
If in a symptomatic patient other abnormalities are not detected, the next step will be lung imaging using ⁶⁷Gallium citrate.
5. ⁶⁷Gallium citrate imaging
Lung imaging using ⁶⁷Ga citrate will be performed in symptomatic subjects with normal chest radiographs and in whom other pulmonary function abnormalities do not account for the symptoms. Subjects having pulmonary parenchymal uptake of the isotope will be evaluated with sputum induction. If there is no pulmonary ⁶⁷Ga uptake, the diagnostic evaluation will not proceed further, and the subject will be scheduled for a one month follow-up visit.
6. Sputum induction All patients who have symptoms and an abnormality on chest film (as specified in Section 7.2.7), or ⁶⁷Ga scan will have sputum induced.
7. Bronchoscopic procedures

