The purpose of this section is to describe the general approach to utilizing the study data for addressing the substantive questions of interest; this is not meant to be an exhaustive list of analytical approaches, variables and outcomes which will be used to make inferences from these data. For example, because only the HIV seropositive groups are relevant to the estimation of the rates of HIV-related conditions, only these groups will be listed under "groups studied." A diagnosis is associated with HIV if: (1) it occurs only in the HIV seropositive group or (2) it occurs at a significantly higher rate in the HIV seropositive group than in the HIV seronegative group. Therefore, some comparisons with the HIV seronegative group are implicit in addressing some of the questions. Unless such comparisons are the major focus of the question, the HIV seronegative group is not explicitly listed under the groups studied. Another variable that is not explicitly mentioned is the Clinical Center. Because this is a multicenter study, the center is a major variable (predictive or confounding variable) that must be included in most of the analyses. Many of the analyses revolve around appropriate regression models. Where appropriate, nonparametric methods will also be used.

Question 1. What are the specific lung diseases associated with HIV infection and what is their prevalence and incidence?

Groups studied:

All HIV seropositive subjects

Predictive variables

HIV antibody status

Stage of HIV infection (clinical and immunologic)

HIV transmission category

Confounding variables

Preventive treatment for infections

AntiHIV therapy

Immunosuppressive drugs

Outcome variables

Presence of specific diseases as defined in Appendix 2 or other diseases

Analysis

Calculation of prevalence and incidence type measures (crude rates) for specific diseases for various subgroups of the population (determined by predictive variables), and estimation of adjusted rates (adjusted for confounding variables) using regression type models. These rates will be combined using appropriate weighting schemes to estimate "standardized" rates.

Comparisons with corresponding rates in the HIV negative group will be made where appropriate to assess whether these conditions are HIV-related (occur only in the HIV seropositive group or occur in the seropositive group with a significantly higher rate than in the seronegative group).

Precision

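### The symptom work-up stops on a criterion worded by HIV-relatedness and not defined consistently for seronegative controls, so lung disease shared by both groups may be verified unequally by serostatus

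*Protocol*

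**What the plan says.** Three trigger symptoms start a work-up under Section 7.2.4. The first is "unexplained cough that persists for more than five days"; the others are unexplained breathlessness and unexplained new fever. The instruction goes to everyone: "each study subject will be alerted to these symptoms and instructed to contact the study office should they develop". For each symptom, "if a reason other than a possible HIV-related pulmonary process can be found (e.g., asthma), the evaluation will not proceed".

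Two later exits depend on judgement. After history, examination and chest film, "the physician investigator may make the clinical decision that the subject has acute bronchitis and elect to empirically treat". At the pulmonary function step, "Abnormalities in pulmonary function such as airways obstruction, or bronchitis, may account for the patient's symptoms", and the subject is then booked for a one-month visit.

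The protocol applies the key term to controls in one place and not in another. Section 7.2.3 says "Subjects in Groups A-1, B-1 and C who develop an HIV-related pulmonary process will continue to be followed at the same intervals", which includes Group C. Footnote 1 to Table 6, on the same schedule rule, names only A-1 and B-1 for this event.

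The results feed a comparison with controls. Section 4 (Rationale) says that linking HIV to lung diseases that do not define AIDS "necessitates evaluation of persons from HIV transmission categories who do not have HIV infection". The introduction to Appendix 1 counts a diagnosis as HIV-associated if it occurs only in seropositives or if "it occurs at a significantly higher rate in the HIV seropositive group than in the HIV seronegative group". Sections 4 and 5 both promise that diagnostic studies will be applied uniformly.

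**The concern.** HIV-relatedness is what the comparison of Groups A and B with Group C is meant to establish, yet here it helps decide who is investigated. Section 4 says that the apparent excess of pyogenic pneumonia and tuberculosis may reflect lifestyle, and gives this as the reason for having controls. Table 1 already labels tuberculosis as HIV-related and pyogenic pneumonia as presumed HIV-related. An evaluator who knows the serostatus could take the same suspected cause as a reason to continue in a seropositive subject and as another explanation in a control.

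A stopped work-up may never yield the specimen that the diagnosis requires. Appendix 2 asks for a positive culture from a lung-derived specimen for pulmonary tuberculosis, and for isolation of a likely pathogen for definite aerobic bacterial pneumonia. Fewer completed work-ups in controls would lower the control rate in the Appendix 1 association rule and in secondary objective 3 (Section 2), with no difference in true incidence.

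**Working it through.** **1. The plan's own figures.** Appendix 3, Table 3.2 gives the only stated precision for seropositive-versus-control disease rates. Inputs: n = 527, 527 and 177 for A, B and C (Table 5B); PCP rates of 5%, 20% and 0% (footnote to Tables 3.1 to 3.3). Half-width = 1.96 × √[p₁(1−p₁)/n₁ + p₂(1−p₂)/n₂].
- A v C: 1.96 × √(0.05×0.95/527 + 0) = 0.0186; stated 0.02.
- B v C: 1.96 × √(0.20×0.80/527 + 0) = 0.0342; stated 0.03.

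Both reproduce, so no stated number is in error. With 0% PCP assumed in controls there are no control cases to miss, and the bias for PCP is nil.

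**2. Are there control cases of other diseases to miss?** Section 3.6 cites 12-month bacterial pneumonia in 14/159 = 9% of seropositive and 6/277 = 2% of seronegative heroin addicts. So there are.

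**3. Illustration of size.** Let the true one-year rate p be equal in A+B (n = 527 + 527 = 1054) and C (n = 177). Let s be the share of control episodes diagnosed relative to seropositives, net of all safeguards. **The documents give no value for s; the values below are assumptions.** I take p from 2% to 9%, the span of the Section 3.6 figures.

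- Spurious difference = p(1−s). Spurious ratio = 1/s, which only restates the assumption.
- Chance of a significant false excess = Φ[(p(1−s) − 1.96·SE₀)/SE₁], with SE₀ from the pooled rate and SE₁ from the separate rates. With no bias this is about 2.5% in that direction.

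Example, p = 5%, s = 0.5: pooled rate = (52.7 + 4.425)/1231 = 0.0464; SE₀ = √[0.0464×0.9536×(1/1054 + 1/177)] = 0.0171; SE₁ = √(0.05×0.95/1054 + 0.025×0.975/177) = 0.0135; Φ[(0.025 − 0.0335)/0.0135] = Φ(−0.63) = 26%.

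| p | s = 0.9 | s = 0.75 | s = 0.5 |
|---|---|---|---|
| 2% | 0.2 points, 3% | 0.5 points, 5% | 1.0 point, 9% |
| 5% | 0.5 points, 4% | 1.25 points, 9% | 2.5 points, 26% |
| 9% | 0.9 points, 5% | 2.25 points, 14% | 4.5 points, 52% |

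Over three years, with cumulative rates 1−(1−p)³ and 1−(1−ps)³, the same n and s = 0.5, the differences are 2.9, 6.9 and 11.7 points for annual rates of 2%, 5% and 9%. The corresponding chances are 32%, 76% and 96%. This ignores deaths and losses.

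**4. Direction in other questions.** Questions 9 and 10 compare seropositives without diagnosed lung disease against seronegatives. A control whose disease is missed still contributes symptoms or reduced function to the comparison as if free of diagnosed disease. That would shrink an HIV excess.

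**The case against.** A reader might infer that controls satisfy the stop rule by definition, so that their evaluation need never proceed. The text does not support that. A reason must be found, and seronegativity is not a reason for a cough. A control whose symptom stays unexplained goes on to chest film, pulmonary function tests and gallium scan. Section 7.2.3 and Table 1 also suggest that HIV-related can be read as a disease label, under which suspected pneumonia or tuberculosis in a control would not be an exit.

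Several safeguards take no account of serostatus. An abnormal film at the symptom visit leads to the Section 7.2.7 algorithms. Controls have the same scheduled films and function tests as A-1 and B-1. Outside records are retrieved (Section 7.2.8). Site reviews check that indicated studies were done (Section 10.1). The bronchitis and airways-obstruction exits do not mention HIV, and the Section 7.2.7 figures are not available to judge. The Section 4 sentence on controls requires them to be evaluated but does not itself say uniformly; other sentences in Sections 4 and 5 do.

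These points remove any claim of certain or large bias. They do not settle the matter:
- Footnote 1 to Table 6 undercuts the disease-label reading.
- The film rule leaves normal-film episodes exposed.
- The instruction to enter later diagnoses follows the sentence on referred fevers, so it is unclear whether it reaches other stops.
- A review of adherence would pass a stop that the rule itself permits.

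**Conclusion.** The concern stands as a risk of differential verification. The stop rule is worded in terms of the exposure under study, covers controls, is applied without stated masking, and has no consistent meaning for Group C. It sits uneasily with the promise of uniform application and feeds directly into the Appendix 1 association rule.

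The documents do not show that control disease is in fact under-diagnosed or that an HIV excess is manufactured. The size is unknown. The illustrative 0.2 to 4.5 points in one year (3% to 52% chance of a false significant excess) rests wholly on assumed s between 0.9 and 0.5, equal true rates of 2% to 9% and the Table 5B numbers; at s = 1 there is no bias. The risk is confined to diseases that occur in both groups, mainly in episodes with a normal film. It does not touch PCP at the assumed 0% control rate, and in Questions 9 and 10 it may act against an HIV effect.

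**What to change.** - Reconcile the Section 7.2.4 stop rule with the uniform-application statements in Sections 4 and 5, so that the reason for stopping is stated without reference to HIV status and is the same for Groups A, B and C. Align Section 7.2.3 and footnote 1 to Table 6 in the same edit. The clinical content of the criterion is for the investigators.
- Record a coded reason and the final diagnosis for every stopped evaluation, in all groups.
- Report work-up completion by group beside each A/B-versus-C disease comparison, with a sensitivity analysis that counts pulmonary diagnoses from stopped evaluations.

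Keep the comparisons of specific diagnoses. Restricting them to history, examination and film would remove culture-defined tuberculosis and definite bacterial pneumonia from objective 3. Counting every stopped evaluation as lung disease would sweep in episodes such as fever with diarrhea.

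The cost is a wording change, one added form field and a little more analysis. If stops are not coded, the bias could be neither measured nor corrected afterwards.

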7.2.5 Follow-up after a non-diagnostic evaluation of suspected pulmonary disease

If the evaluation does not provide a diagnosis and the clinical course is stable or improving, the patient will be observed. If he/she is severely ill or rapidly deteriorating further evaluation will be undertaken as determined by the clinical circumstances. All subjects who undergo a diagnostic evaluation for suspected pulmonary complications will return for a follow-up one month after hospital discharge for inpatients or one month after the symptom evaluation visit for outpatients.

Patients will be instructed to call the study office if they feel there is no symptomatic improvement after one week or sooner if they feel the symptoms are worsening. Patients who appear unreliable or ill will be telephoned by a member of the study team as frequently as needed to determine their progress until stable or improving.

Subjects who do not have symptoms or whose symptoms are improving will return for a one month follow-up visit. If the chest radiograph and pulmonary function tests demonstrate no deterioration the subject will revert to the routine protocol.

If the symptoms worsen or do not improve, the subject will return before the one month follow-up visit for a repeat physical examination, and chest radiograph. If the chest radiograph abnormality is worse, the patient will be considered to have deteriorated. Patients with documented deterioration will undergo repeat sputum induction, bronchoscopy and/or open lung biopsy. If no deterioration is documented, the subject will continue to be monitored by telephone calls and reevaluated as needed until deterioration, stability or improvement

is noted. After the one month follow-up clinic visit, stable and improved patients will revert to the routine study protocol.

7.2.6 One month follow-up visit

In addition to follow-up after evaluations for suspected pulmonary complications, one month follow-up visits will be scheduled for subjects with: 1) fever, no respiratory symptoms, and a normal chest radiograph; 2) respiratory symptoms, a normal chest film, and normal 67Ga scan; 3) respiratory symptoms, and other abnormalities in pulmonary function that account for the symptoms; or 4) one month after hospital discharge for subjects admitted with respiratory symptoms; 5) one month after the symptom evaluation visit for outpatients if respiratory symptoms persist; or 6) one month after start of therapy for lung diseases.

For all of the above (numbers 1-6), the one month follow-up visit will include:

1. Interval visit questionnaire. In addition, information from relevant medical records will be abstracted.
2. Physical examination. The physical examination will be the same as that performed for routine visits and will be recorded on the same form.
3. Pulmonary function tests (lung volumes, expiratory flows and DLCO).²
4. Chest radiographs (standard frontal and lateral views).³
5. Blood tests. All subjects who had blood tests performed at the symptom evaluation visit will have the following blood tests:

T-cell subset determination (if not done within 3 months of the visit).

Complete blood count and differential, ESR, SMAC panel (including LDH).

Serum to be frozen at -70°.

6. Obtain induced sputums for PCP and AFB for all subjects diagnosed with PCP or infection with M. tuberculosis (not

^{2/} If the PFTs and chest film were normal at the symptom evaluation visit and the symptoms have resolved, these evaluations do not need to be repeated at the one-month follow-up visit.

^{3/} Same as footnote 2.

atypical mycobacteria) and analyze the sputum for both PCP and M. tuberculosis q one month until the subject is negative for the organism originally identified (either PCP or M. tuberculosis).

At baseline, a one month follow-up visit will be scheduled for subjects with: 1) DLCO <75% at the initial visit; and/or 2) abnormal chest film at the initial visit. The one month evaluation will include only a repeat of the abnormal test (DLCO and/or chest film). If the abnormality is stable or improved no further evaluation will be performed. If it is worse then evaluation will proceed.

A one month follow-up visit can substitute for a routine assessment if it is done \pm 3 months for Groups A-1 and B-1 or \pm 1 month for Groups A-2 and B-2 from the date of scheduled studies and tests are complete. This may in some cases require that in addition to the usual one month follow-up studies HIV antibody, skin test and sputum induction may be performed.

7.2.7 Diagnostic algorithms

The following algorithms will be used in the diagnostic evaluations of patients with symptoms or findings:

7.2.8 Procedures for Obtaining Clinical Data From Facilities Outside of the Clinical Centers

Although participants must agree, as a condition of entry into the study, to be evaluated at a Clinical Center in the event of possible pulmonary complications, it is likely that some participants will undergo evaluation at facilities other than the Clinical Centers. In order to retrieve data from such evaluations, the following procedures will be used:

1. Participants will sign a release of information form at the time of initial enrollment into the study. This will be used subsequently to obtain medical records for review if necessary.
2. Participants will be given an identification card with the Clinical Center's number. They will be instructed to inform any nonstudy physician/caregiver to contact the Clinical Center as soon as possible in the event that a possible pulmonary complication arises.

Figure 2

Evaluations of Radiographic Abnormalities - Focal Consolidation

[figure not shown]

Figure 3
Evaluation of Radiographic Abnormalities - Pleural Effusion

[figure not shown]

Figure 4

Evaluation of Radiographic Abnormalities - Intrathoracic Adenopathy

[figure not shown]

Figure 5

Evaluation of Radiographic Abnormalities - Cavitary Lesion

[figure not shown]

Figure 6

Evaluation of Radiographic Abnormalities - Mass Lesion or Solitary Pulmonary Nodule

[figure not shown]
[figure not shown]

Figure 7

Evaluation of Radiographic Abnormalities - Diffuse Process of Focal Interstitial Pattern

3. When a nonstudy physician/caregiver contacts the center the study's purposes will be described and relevant procedures and algorithms explained. A request will be made that these be followed. Whenever possible center services and expertise should be made available to the noncenter physician.
4. Subsequent to the completion of the participant's evaluation, every effort will be made to obtain the relevant medical records. In addition, related chest radiographs, pathologic and microbiologic (e.g., stained sputum smears for P. carinii) specimens and pulmonary function data will be requested for review at the Clinical Center. Data gathered as the result of such a review will be entered after validation on the appropriate study forms and transmitted to the Coordinating Center.

8. Data Collection, Entry and Management

